## Appendix 9 Module 3 Schedule of Assessments

	Module 3 (RXC004 monotherapy intermittent schedules) Schedule of Assessments									
	Pre-Screening	Screening	Cycle 0 (3-7 days)	Cycle 1 (21 day cycle)		Cycle X Day 1 (21 day cycles)	IP Discontinuation	30 day Safety Follow-up 	PFS Follow-up	
Window	n/a	-28 to -1	D1	D1	D11(-1d)	+/- 3d	Within 7 days of discontinuation	+/- 3d	q6w (+/- 1 week)	
Pre-Screening informed consent (optional)	X									
Diagnostic / Archival tumour tissue	X	X (optional)								
Genetic screening for RNF43/RSPO aberrations (optional)	X									
Informed consent		X								
Pharmacogenetics (optional consent and blood sample) i		X								
Demography & baseline characteristics		X								
Smoking status & alcohol consumption		X								
Medical/surgical history		X								
Inclusion/exclusion criteria**		X								
Bone Scan		X	As clinically indicated							
Physical examination a		X	X	X		X	X			

Module 3 (RXC004 monotherapy intermittent schedules) Schedule of Assessments									
	Pre-Screening	Screening	Cycle 0 (3-7 days)	Cycle 1 (21 day cycle)		Cycle X Day 1 (21 day cycles)	IP Discontinuation	30 day Safety Follow-up 	PFS Follow-up
Window	n/a	-28 to -1	D1	D1	D11(-1d)	+/- 3d	Within 7 days of discontinuation	+/- 3d	q6w (+/- 1 week)
ECOG/WHO performance status		X	X	X		X	X		
Pregnancy test (WOCBP only)		(X)	(X)	(X)		(X)			
Vital signs (including height and weight) b		X	X	X	X	X	X	X	
Clinical chemistry / Haematology		X	X	X	X	X	X	X	
Urinalysis*		X	X	X	X	X			
ECG		X	X	X	X	X h	X		
DXA scan (including VFA*** at baseline)		X				Cycle 2, 4 and 7, and every third cycle thereafter			
Skin punch biopsy (mandatory)			X m		X m	X m			
Newly acquired tumour biopsy (optional)		X			X g				
Blood samples for bone turnover biomarkers		X			X	X	X		
Blood sample for circulating soluble factors c			X		X	X			
Blood sample for PBMC (viable cells) c			X		X	X			

Module 3 (RXC004 monotherapy intermittent schedules) Schedule of Assessments									
	Pre-Screening	Screening	Cycle 0 (3-7 days)	Cycle 1 (21 day cycle)		Cycle X Day 1 (21 day cycles)	IP Discontinuation	30 day Safety Follow-up l	PFS Follow-up
Window	n/a	-28 to -1	D1	D1	D11(-1d)	+/- 3d	Within 7 days of discontinuation	+/- 3d	q6w (+/- 1 week)
Fresh blood for PD analysis d			X		X	Cycle 2 Day 1 only			
Blood sample ctDNA analysis e			X		X	X	X		
Blood sample ctRNA analysis e			X		X	X	X		
RECIST 1.1 assessments (by CT/MRI) j		X	Every 6 weeks +/- 1 week from Cycle 1 Day 1 until RECIST1.1 defined disease progression						
Vitamin D3 and Calcium supplements		Patients should commence vitamin D3 (cholecalciferol 800IU QD) and calcium 1000-1500 mg QD supplements from ICF signature until RXC004 discontinuation							
Denosumab dosing o		120 mg sc. denosumab QM from C0D1 until RXC004 discontinuation							
RXC004 dosing			X	2 mg QD intermittent schedule k					
RXC004 PK f			X	X	X	X	X		
Concomitant medication		X	X	X	X	X	X	X	
Adverse events		X	X	X	X	X	X	X	
Taste Assessment m		X	At each visit – only if patient reports a taste disturbance						
Patient diary card review				X	X	X	X		
Subsequent anti-cancer therapy							X	X	X

Footnotes - General

Assessments made on Day 1 of each cycle are to be conducted prior to RXC004 administration, unless specified otherwise.

Additional assessments may be conducted as clinically indicated.

A tolerance of +/-1 day will be permitted for all study visits and a tolerance of -1 day for all assessments relative to the study visit, unless specified otherwise.

\* Female patients, if fertile, will require a serum pregnancy test at Screening and urine pregnancy on Day 1 of each cycle

\*\*Eligibility criteria to be re-checked at Cycle 1 prior to dose administration.

\*\*\*A lateral T & L spine assessment if a Vertebral Fracture Assessment (VFA) cannot be completed locally

- a A full physical examination is required at Screening and prior to Day 1 of each cycle ; Symptom-directed physical examination is acceptable at other time-points
- b Vital signs (heart rate, BP, temperature and respiration rate) will be assessed pre-dose and up to 1 hour after the RXC004 administration. Patient status will be monitored during RXC004 administration and repeat vital signs will be taken if needed. Height is required at screening only. Weight will be recorded at Screening and on Day 1 of each cycle.
- c All samples should be collected pre-dose
- d Fresh blood samples to be collected from UK sites only. All samples should be collected pre-dosing.
- e Samples should be collected pre-dose for all samples.
- f Patients will have PK blood sampling conducted at the following sample times
  - Cycle 0: Day 1 - Predose, then 30 mins, 1 h, 2 h, 4 h, 6 h, 8 h, 10 h, 12 h, 24 h, and 48 h post-dose.
  - C1D11: Predose, then 30 mins, 1 h, 2 h, 4 h, 6 h, 8 h, 10 h, 12 h & 24 h
  - Cycle X, Day 1 - A single pre-dose sample will also be taken on subsequent samples on Day 1.
- g The SRC may advise on adjusted time-points. The actual time for each blood draw must be accurately recorded.
- g An optional 'on treatment' biopsy during Cycle 1 Day 11 treatment visit, preferably 4-6hrs post dose and from the same site as the baseline biopsy sample. The actual time of collection should be accurately recorded.
- h Triplicate ECGs should be collected as follows;
  - Cycle 0: Day 1 – Pre-dose (within 30 mins of first dose), then 1 h ± 10 mins and 12 h ± 30 mins post-dose
  - Cycle 1, Day 11- Predose (within 30 mins of dose), then 1 h ± 10 mins and 12 h ± 30 mins post-dose
  - Cycle X, Day 1 - Pre-dose (within 30 mins of dose)
- i Consenting patients will have a 10 mL blood sample taken for preparation of a germ-line DNA sample at Screening (recommended time-point only).
- j CT (preferred) or MRI, each preferably with IV contrast. It is strongly recommended to maintain use of the same imaging modality (CT or MRI), acquisition protocol, facility and scanner across all imaging time points per patient. Note that where there is a rationale for assessment of bone lesions that develop after study start, these assessments will be performed as part of the CT or MRI assessment and will not require additional radiological bone scan assessment. Additional scans may be performed to confirm a Complete Response (CR) or Partial Response (PR) or disease progression (PD) as per appropriate response assessment guidelines. Any requirement for confirmatory scans will typically be performed at the next protocolled assessment time point. Other assessments e.g. whole body MRI or PET, are not protocol mandated, but may be performed as clinically indicated and at request of Investigator.
- k Arm 1 treatment schedule is 2mg QD RXC004 for 4 days, followed by 3 days off, repeated for 21 days per cycle of treatment. Arm 2 treatment schedule is 2mg QD RXC004 for 2 weeks, followed by 1 week off. Further arms investigating other intermittent schedules may be added after review by SRC. Results for chemistry and haematology labs must be available before starting a new treatment cycle (within 3 days) and reviewed by the treating physician or Investigator prior to dosing
- l Follow up assessments should be performed 30 days after last dose of RXC004
- m Mandatory skin punch biopsies will be collected from all patients. All patients should consent to two skin punch biopsies – pre-dose on C0D1 (baseline) and one 'on study treatment' biopsy on either C1D11 or C2D1. The first 3 patients in a given Arm will also have a skin punch biopsy on C1D11 (RXC004 dosing day sample) and the last 3 patients will have a skin punch biopsy pre-dose on C2D1 (off RXC004 sample). Patients will have skin punch biopsies conducted at the following sample times (the actual time of collection should be accurately recorded);
  - All patients - C0D1 - Predose
  - Patients 1 to 3 within an Arm - C1D11 - 4-6 hrs post dose
  - Patients 4 to 6 within an Arm - C2D1 - Predose
- n A taste assessment (consisting of a specific set of questions) will be performed at screening and at each study visit when patient reports a taste disturbance. Please see Section 4.2 for more details
- o All patients must receive denosumab before first dose of RXC004. 120 mg sc denosumab should be administered approximately once every month from C0D1 until RXC004 discontinuation. Investigators may delay subsequent denosumab doses until the next scheduled visit providing that there is no significant increase in  $\beta$ -CTX compared to baseline, according to Investigator judgement

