## 2 SELECTION OF STUDY POPULATION AND RESTRICTIONS

### 2.1 Inclusion Criteria

#### 2.1.1 Core Inclusion Criteria

For inclusion in all modules of the study, all patients must fulfil all of the following criteria:

1. Ability to give written informed consent prior to any study-specific screening procedures, sampling and analyses; including access to all archival tumour tissue taken within the last 18 months, with the understanding that the consent may be withdrawn by the patient at any time without prejudice
2. Capable of understanding the protocol requirements, is willing and able to comply with the study protocol procedures, restrictions (Section 2.3) and has signed and dated the informed consent document
3. Aged at least 18 years at time of screening.
4. Patients must have histological or cytological confirmation of advanced malignancy not considered to be appropriate for further conventional treatment
5. Evaluable disease, either measurable on imaging, or with informative tumour marker(s), as assessed by RECIST 1.1 (Appendix 4) or other relevant response assessment criteria for tumour type. For RECIST 1.1, patients should have at least 1 lesion that qualifies as a RECIST 1.1 target lesion at baseline (within 28 days of the first dose). The use of scans obtained as part of standard clinical practice, prior to informed consent, will be accepted if they comply with RECIST 1.1 criteria and have been performed within the 28-day screening period.
6. Patients must have recovered from toxicities of prior therapies. (i.e. to CTCAE  $\leq$  grade 2) apart from alopecia
7. Eastern Cooperative Oncology Group (ECOG) (Appendix 3) or World Health Organisation (WHO) performance status 0 or 1 with no deterioration over the previous 2 weeks and an estimated life expectancy of greater than 12 weeks
8. Organ Function Requirements - Patients must have adequate organ functions as defined below:
  - $AST/ALT \leq 2X$  ULN (upper limit of normal) [with no underlying Liver Metastasis]
  - $AST/ALT \leq 3X$  ULN [with underlying Liver Metastasis]
  - Total Bilirubin within normal range
  - Serum Creatinine  $\leq 1.5X$  ULN
  - $ANC \geq 1500/\mu L$
  - Platelets  $> 100,000/\mu L$
  - $Hb > 9g/dL$

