**Procedures for handling patients incorrectly initiated on investigational product:**

Patients who do not meet the inclusion/exclusion criteria should not, under any circumstances, be enrolled or receive study medication. There can be no exceptions to this rule.

Where patients that do not meet the inclusion/exclusion criteria are enrolled in error or incorrectly started on treatment, or where patients subsequently fail to meet the study criteria post initiation, the Investigator should inform the Study Physician immediately.

Any patient who is found to have failed to comply with all the selection criteria, but has not started treatment, will be removed from the study following completion of safety follow-up activities.

Any patient started on treatment in error, as he/she has subsequently been found to have failed to comply with all the selection criteria, will undergo a risk/benefit assessment by the SRC; if the patient is judged to be receiving clinical benefit, the investigator may choose to continue to dose them with the investigational drug.

Every effort should be made to keep all patients, whether eligible or ineligible, in the study until completion of safety follow-up activities.

The Study Physician is to ensure all such contacts are appropriately documented.

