### **5.3.3 Module 2: Ascending Combination MAD**

Module 2 will enroll three patients into a cohort with follow up for AEs and DLT.

Patients will start with a single dose of RXC004 followed by a washout of 3-7 days (Cycle 0). RXC004 and nivolumab will commence at Cycle 1. The first cohort will be daily RXC004 and 480 mg nivolumab every 4 weeks (28 days).

The DLT period will be until the end of Cycle 1. Dose escalation will continue in a 3+3 design until MTD/MFD has been reached in the combination. Decisions on doses and/or schedules of RXC004 in combination will be made in discussion with the SRC.

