### 5.4.4 RXC004 Intermittent Schedules

Module 3 will enroll 6 evaluable patients per Arm, with follow up for PK, pharmacodynamics and AEs.

An evaluable patient in Module 3 is defined as a patient that has received study treatment and either:

- Has completed minimum safety evaluation requirements and has received 100% of the specified RXC004 dose in Cycle 0 and at least 80% of the intended dose of RXC004 during Cycles 1 and 2.

- Has permanently discontinued study treatment due to a related adverse event

Subjects will start with a single dose of RXC004 followed by a washout of 3-7 days (Cycle 0). RXC004 schedules will commence on Cycle 1, Day 1. Each treatment cycle will be 21 days. Study treatment will continue until disease progression, intolerable toxicity or withdrawal of consent. Module 3 will start with two treatment Arms of intermittent RXC004 schedules;

- Arm 1 – 2mg QD RXC004 for 4 days, followed by 3 days off, repeated weekly for 21 day treatment cycles
- Arm 2 – 2mg QD RXC004 for 2 weeks, followed by 1 week off (21 day treatment cycles)

Patient enrolment into Arms 1 and 2 will run concurrently.

Further RXC004 monotherapy arms may be opened after review of safety and tolerability information from Arms 1 and 2, relevant data from Modules 1 and 2 and any emerging preclinical data.

[figure not shown]
Mandatory skin punch biopsies will be taken from all patients in Module 3 at baseline and while receiving treatment for analysis of pharmacodynamic markers of Wnt pathway inhibition, alongside PK sampling (see Schedule of Assessments in Appendix 9).

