**Footnotes - General**

Assessments made on Day 1 of each cycle are to be conducted prior to RXC004 administration, unless specified otherwise.

Additional assessments may be conducted as clinically indicated.

A tolerance of +/-1 day will be permitted for all study visits and a tolerance of -1 day for all assessments relative to the study visit, unless specified otherwise.

\* Female patients, if fertile, will require a serum pregnancy test at Screening and urine pregnancy on Day 1 of each cycle.

\*\*Eligibility criteria to be re-checked at Cycle 0 prior to dose administration.

^^ Morning after an overnight fast

++The PK from Cy0D1 will be analysed with fast turnaround, sites will be informed if the exposure level is deemed inappropriate to start continuous treatment

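### In Modules 2 and 3 the eligibility re-check is set at Cycle 1, after the first RXC004 dose at Cycle 0, whereas Module 1 re-checks before that dose

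*Protocol*

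**What the plan says.** All three modules open with a single RXC004 dose on Cycle 0 Day 1. For Module 3, Section 5.4.4 reads "Subjects will start with a single dose of RXC004 followed by a washout of 3-7 days (Cycle 0"; Section 5.3.3 says the same for Module 2.

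The schedules place the eligibility re-check differently:

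- **Module 1 (Appendix 1):** inclusion/exclusion is marked at Screening and Cycle 0, with the footnote "Eligibility criteria to be re-checked at Cycle 0 prior to dose administration".
- **Modules 2 and 3 (Appendices 2 and 9):** inclusion/exclusion is marked at Screening only (day -28 to -1), with the footnote "Eligibility criteria to be re-checked at Cycle 1 prior to dose administration".

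Appendices 2 and 9 also schedule physical examination, ECOG, pregnancy test, vital signs, chemistry/haematology, urinalysis and ECG at Cycle 0 Day 1, under the general rule "Assessments made on Day 1 of each cycle are to be conducted prior to RXC004 administration, unless specified otherwise".

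Section 3.6 forbids, without exception, giving study medication to a patient who does not meet the criteria. For a patient already dosed it says only that "where patients subsequently fail to meet the study criteria post initiation, the Investigator should inform the Study Physician immediately", and it sends patients started in error to a risk/benefit assessment by the Safety Review Committee (SRC).

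**The concern.** A re-check placed after the first dose cannot enforce a rule that ineligible patients must not be dosed. It can only find them afterwards. It also applies entry limits to values measured after exposure. Some limits are tight: "Total Bilirubin within normal range" fails on any elevation, and ANC must be at least 1500/µL. A value just outside such a limit at Cycle 1 could be a drug effect, yet it would be read as an entry failure.

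Two things are at stake. One is the safeguard at first exposure. The other is the composition of the evaluable set that drives Module 2 escalation: the protocol orders a post-dose eligibility check and does not say what follows from failing it.

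**Working it through.** There is no planned figure to reproduce. The check is a comparison of texts, some day arithmetic and one labelled illustration.

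**1. Order of events**

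| | Module 1 | Module 2 | Module 3 |
|---|---|---|---|
| Inclusion/exclusion marked | Screening, Cycle 0 | Screening | Screening |
| First RXC004 dose | Cycle 0 Day 1 | Cycle 0 Day 1 | Cycle 0 Day 1 |
| Length of Cycle 0 | 6-10 days | 3-7 days | 3-7 days |
| Re-check against first dose | before | 3-7 days after | 3-7 days after |

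A check meant to precede nivolumab could explain Module 2 but not Module 3, which has no nivolumab and carries the same footnote.

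**2. Age of the data**

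- *Repeated at Cycle 0 Day 1* (laboratory tests, ECG, ECOG, pregnancy test): 0 to 1 day old at the dose, given the one-day tolerance.
- *Screening only* (β-CTX, vitamin D, DXA/VFA, bone scan, tumour imaging): up to 28 days old at first dose and 28 + 3 = 31 to 28 + 7 = 35 days old at Cycle 1 Day 1. The Cycle 1 re-check does not refresh these, since none is scheduled that day.

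**3. Does other text force a pre-dose review?**

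- *Module 2:* footnote k of Appendix 2 requires laboratory results to be reviewed before a nivolumab infusion. Nivolumab starts at Cycle 1.
- *Module 3:* footnote k of Appendix 9 says "Results for chemistry and haematology labs must be available before starting a new treatment cycle (within 3 days". It is attached to the intermittent-schedule cell, not the Cycle 0 dose cell, and does not mention the eligibility limits.

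Neither requires Cycle 0 Day 1 results to be compared with the criteria before the first dose.

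**4. Module 2 evaluability**

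- Section 5.3.6 defines a DLT as arising from Cycle 1 Day 1 to Day 28.
- Section 5.3, Section 3.1.3 and SAP Section VI.J.4 count DLTs in Cycle 0.
- Section 3.1.3 otherwise requires at least 66% of the Cycle 1 RXC004 dose and the full nivolumab infusion on Cycle 1 Day 1. It replaces a withdrawn patient who is not evaluable.

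A patient stopped at the Cycle 1 re-check would miss the 66%. Under Section 5.3.6 a Cycle 0 toxicity would not count as a DLT, so the patient would be non-evaluable and replaced. Under the other three texts a Cycle 0 DLT would keep the patient in. A change below DLT grade, such as a slightly raised bilirubin, leads to replacement under either reading if the patient is stopped.

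**5. Module 3 evaluability**

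Section 5.4.4 and SAP Section VI.J.5 keep as evaluable a patient who permanently discontinues for a related adverse event. Section 4.1 requires a laboratory deterioration that is the reason for discontinuation to be reported as an AE. The route remains only if the reason is recorded as ineligibility or the event is judged unrelated.

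**6. Size**

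One patient is 1/3 = 33% to 1/6 = 17% of a Module 2 cohort, and 1/6 = 17% of a Module 3 arm. The documents give no frequency.

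Illustration for Module 2 only. Let p be the true DLT rate and f the share of patients with a DLT who are instead classed as ineligible and replaced. Both are assumptions. The rate among evaluable patients becomes p' = p(1 - f)/(1 - pf). The 3+3 rule escalates with probability (1 - p')³ + 3p'(1 - p')² × (1 - p')³.

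| p | f = 0 | f = 10% | f = 25% | f = 50% |
|---|---|---|---|---|
| 20% | 0.709 | 0.744 | 0.798 | 0.887 |
| 33% | 0.434 | 0.480 | 0.557 | 0.714 |
| 40% | 0.309 | 0.351 | 0.428 | 0.600 |

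For p = 33% and f = 10%, p' = 0.297/0.967 = 30.7%; at f = 50%, p' = 0.165/0.835 = 19.8%. A re-check before the Cycle 0 dose makes f = 0 for this route.

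**The case against.** The strongest reply is that little is missing beyond a second mark on a schedule. Section 3.6 already bars dosing ineligible patients, Section 5.3.2.2 ties the exclusion criteria to receiving treatment, and core inclusion criterion 9 requires a negative pregnancy test before dosing. Fresh laboratory tests, ECG and performance status are available at Cycle 0 Day 1. In Module 2 a check before the first nivolumab infusion is defensible. All of that stands. It shows that the rule exists, not that anyone is told to apply it to the Cycle 0 results, which Appendix 1 does for Module 1.

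A reader might infer four stronger things that the documents do not support:

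- *That patients are dosed on laboratory, ECG or performance data up to 28 days old.* Those are repeated before the Cycle 0 dose; only the screening-only items can be that old.
- *That failing the re-check means withdrawal and replacement.* No text says so. Section 3.6 refers such cases to the Study Physician and patients started in error to the SRC, after which dosing may continue.
- *That these patients drop out of the safety analysis.* The Safety Population (SAP Section VI.J.1) takes everyone with at least one dose, and under Section 3.2 the SRC may weigh other AEs.
- *That new diarrhoea after the Cycle 0 dose makes a patient ineligible.* That exclusion concerns persistent diarrhoea before enrolment.

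**Conclusion.** The point holds as an inconsistency between schedules with a safety-relevant consequence. In Modules 2 and 3 the last formal eligibility decision before first exposure is at Screening, and the re-check comes 3-7 days after the first dose, on values the drug may have altered.

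The effect on evaluability is a possible route, not a stated rule. It is open mainly in Module 2, where Section 5.3.6 conflicts with Sections 3.1.3 and 5.3, and largely closed in Module 3. Where it operates, it affects the evaluable set and the escalation decision, not the AE tables.

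Its size cannot be established. The per-patient weights of 17-33% are cohort fractions, and the escalation probabilities rest on assumed values of p and f. The amendment is worth making because the correction is cheap and copies the protocol's own Module 1 practice, not because a bias of known size has been shown.

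**What to change.** 1. In Appendices 2 and 9, set the footnote ** re-check at Cycle 0 Day 1 before the first RXC004 dose and mark inclusion/exclusion at Cycle 0, as in Appendix 1. State which of the Cycle 0 Day 1 results already scheduled must be reviewed first.
2. Any Cycle 1 check before nivolumab in Module 2 may stay, labelled as a separate pre-treatment check.
3. Reconcile the Module 2 DLT window: Section 5.3.6 against Sections 3.1.3 and 5.3 and SAP Section VI.J.4.
4. Reconcile footnote ** with Sections 3.1.3, 3.6 and 5.4.4, so that a change arising after the Cycle 0 dose does not by itself make a patient replaceable as ineligible in the evaluable set. How such changes are managed clinically is for the sponsor to settle.

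The cost is amendment wording and one mark per schedule. No test is added, but sites will need Cycle 0 Day 1 results before dosing. The change does not refresh the screening-only items.

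SAP Tables 2 and 3 already list actual doses for Modules 2 and 3, so some patients will have entered under the present text. For them, the study report should list everyone dosed in Cycle 0 but not in Cycle 1, with the recorded reason and evaluability status.

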### TV in male C57BL/6 mice bearing B16F10 tumours

### TV in male NOD SCID mice bearing SNU-1411 tumours

Time course of RXC004 effects on tumour size in in two models with two dosing schedules QD: once daily, 5 on/2 off: five days dosing with 2 days non-dosing. Statistical comparisons by ANOVA.  $P < 0.05$  denoted by “\*”,  $P < 0.01$  denoted by “\*\*”,  $P < 0.001$  denoted by “\*\*\*” and  $P < 0.0001$  as “\*\*\*\*”.

The two schedules were selected following compartmental modelling of plasma PK data from all dose cohorts in Module 1, in which a naïve pooled approach was employed. Model estimates were used to simulate the exposure of four different dose sequential regimens: 5 days on/2 days off; 4 days on/3 days off; 2 weeks on/1 week off and 2 weeks on/2 weeks off. Of these four potential intermittent treatment regimens the 4 days on/3 days off and 2 weeks on/1 week off regimens were selected to be studied in Module 3 because over a 21-day

treatment cycle these respectively give 14% and 24% of time below the  $IC_{50}$  for Wnt pathway inhibition and at least 72 % of time above the target  $C_{min}$  of >3-fold  $IC_{50}$  in patients.

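### The ±3-day window on Module 3 Cycle X Day 1 conflicts with Arm 1's 3 days off and lets its off-drug C2D1 samples be taken 24 or 48 hours after a dose

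*Protocol*

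**What the plan says.** **Schedules.** Protocol 5.4.4 gives Arm 1 as 2 mg daily "for 4 days, followed by 3 days off, repeated weekly for 21 day treatment cycles", and Arm 2 as "2mg QD RXC004 for 2 weeks, followed by 1 week off (21 day treatment cycles". Appendix 9 footnote k repeats the first: "Arm 1 treatment schedule is 2mg QD RXC004 for 4 days, followed by 3 days off".

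**Visit window.** In the Appendix 9 table, the column headed "Cycle X Day 1 (21 day cycles" carries a window of plus or minus 3 days. The general footnotes say "A tolerance of +/-1 day will be permitted for all study visits", but only where nothing else is specified, so the column's own window governs C2D1. The C1D11 visit has a window of minus 1 day only.

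**Samples.** Every patient has a baseline skin biopsy. The first three in an arm have the second one on C1D11, a dosing day. For the others, "the last 3 patients will have a skin punch biopsy pre-dose on C2D1 (off RXC004 sample". Footnote f adds one pre-dose PK sample on Day 1 of later cycles. On order, "Assessments made on Day 1 of each cycle are to be conducted prior to RXC004 administration, unless specified otherwise".

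**Modelled exposure.** Protocol 5.4.5 says of the two schedules that "these respectively give 14% and 24% of time below the" IC50, and that each keeps no less than 72% of the cycle above three times IC50.

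Footnotes f and m require actual sampling times to be recorded, and Protocol 6.5 requires exact dosing times. I found no minimum time since last dose for the C2D1 samples, and nothing that closes the early side of the window.

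**The concern.** Arm 1's last off-period in a cycle is exactly as long as the early side of the visit window. A visit can therefore comply with the schedule table and still fall one ordinary dosing interval after a dose, while footnote m treats its biopsy as off drug. The on-drug visit does not have this problem: Days 10 and 11 are dosing days in both arms, so a minus 1 day window keeps C1D11 on drug.

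Module 3 asks what short treatment breaks do to PK, Wnt inhibition and tolerability. Footnote m contrasts on-drug and off-drug biopsies in groups of three. If an Arm 1 off-drug sample is really an on-treatment trough, the contrast is blurred and the arm could appear to sustain pathway inhibition through a break that had not yet happened.

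**Working it through.** **Inputs.** Schedules (Protocol 5.4.4); window (Appendix 9 table); half-life in man 11 to 13 h (5.4.5); 14% and 24% of the cycle below IC50 and no less than 72% above three times IC50 (5.4.5); trough at 2 mg daily more than 3-fold IC50 (5.4.3); three off-drug biopsies per arm (footnote m).

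**Step 1: calendar, no model needed.** Arm 1 doses on Days 1–4, 8–11 and 15–18. Arm 2 doses on Days 1–14. Nominal C2D1 is Day 22. Hours since last dose = 24 × (visit day − last dosing day). For Arm 1 on Day 19: 24 × (19 − 18) = 24 h. For Arm 2 on Day 19: 24 × (19 − 14) = 120 h.

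**Step 2: reproduce the plan's exposure figures.** Arm 1 repeats weekly, with 96 h from the last dose of one block to the first of the next.
- Time below IC50 per week: 0.14 × 168 = 23.5 h.
- IC50 crossing: 96 − 23.5 = 72.5 h after the last dose.
- The same crossing in Arm 2: (192 − 72.5)/504 = 23.7%, against 24% stated.
- Three times IC50 is reached log2(3) × half-life before the crossing, at 55.0 h (half-life 11 h) or 51.9 h (13 h). Time above it is 1 − (96 − 55.0)/168 = 75.6% or 73.7% in Arm 1, and 1 − (192 − 55.0)/504 = 72.8% or 72.2% in Arm 2. The plan says no less than 72%.

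One crossing time, fitted to the 14%, therefore recovers the other two figures.

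**Step 3: concentration at each permitted early visit.** Multiple of IC50 = 2^((72.5 − h)/half-life).

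| C2D1 visit | Arm 1 off-days before it | Arm 1 h since last dose | Arm 1 multiple of IC50 | Arm 2 off-days before it | Arm 2 h since last dose |
|---|---|---|---|---|---|
| Day 19 (−3) | 0 | 24 | 13–21 | 4 | 120 |
| Day 20 (−2) | 1 | 48 | 3.7–4.7 | 5 | 144 |
| Day 21 (−1) | 2 | 72 | about 1.03 | 6 | 168 |
| Day 22 (nominal) | 3 | 96 | 0.23–0.29 | 7 | 192 |

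Arm 2 at 120 h is at 0.05–0.08 × IC50, still off drug.

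**Step 4: ratio of 24 h to 96 h in Arm 1.** 2^(72/13) = 46.5 and 2^(72/11) = 93. This needs only the half-life and mono-exponential decline, not the crossing time.

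**Step 5: sensitivity.** Suppose the 24 h trough were exactly 3 × IC50. The crossing would then be at about 41 to 45 h, and Arm 1 would spend 31 to 33% of the week below IC50. That does not match the stated 14%; the protocol says more than 3-fold, so 3 is only a lower bound. Under it, the 48 h sample would be at 0.66–0.83 × IC50. The 24 h finding therefore holds either way, while the 48 h finding rests on the 14% calibration.

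**Step 6: share.** One early visit among three off-drug biopsies is 1/3 of the Arm 1 set.

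**The case against.** Several points limit the reach of this, and most of them stand.

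- **Lost off-days.** A reader might infer that the window removes Arm 1's break, giving eight daily doses in a row (Days 15–18, then four from Day 19). The documents do not establish that. The window is for visits. Footnote k still states 3 days off, Protocol 3.5 says the timing of administration may not be changed, and 5.4.7 bars other dose adjustments without Sponsor agreement. On the other side, Day 1 assessments precede dosing, and footnote h puts the Cycle X Day 1 ECG within 30 minutes of a dose. Together these imply that dosing goes with the visit. What stands is a conflict between passages.
- **If dosing stays on the calendar.** A Day 19 sample is then pre-dose only in a stretched sense, three days before the next dose. That is a fair criticism of the wording, but nothing in the text excludes the sample, and it is still 24 h after the last dose.
- **All of Module 3.** A reader might extend the mislabelling to both arms. Arm 2 is at least 120 h off drug. In SAP IV.A, the Module 3 dose-schedule table lists only 2 weeks on/1 week off, and the completed-cycle rule in SAP IX.A uses 14 dosing days, whereas an Arm 1 cycle has 12.
- **No later correction possible.** A reader might infer this from the nominal-visit and nominal-time summaries in SAP VI.D and X. Actual times are recorded, so an early sample can be identified. SAP VI.A says biopsy data are reported from a vendor database, so those two sections are not shown to govern the biopsy. What stands is that no stated rule uses the recorded times.
- **Weight.** Protocol 7.3.3.3.1 lists the skin biopsies as exploratory, and no hypothesis is tested. Pharmacodynamic change is nevertheless a secondary objective in 1.9.2.

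**Conclusion.** The point holds for Arm 1. The Cycle X Day 1 window conflicts with that arm's stated off-days and with the off-drug label on the C2D1 biopsy. The day and hour counts (24 or 48 h instead of 96 h) need no assumption beyond a constant dosing hour.

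The pharmacological size is derived here, not stated in the documents. It assumes mono-exponential decline, a half-life of 11 to 13 h and a crossing near 72.5 h. On that basis the samples at 24 and 48 h are above IC50, the one at 72 h is borderline, and the 24 h level is about 47 to 93 times the 96 h level. One early visit affects a third of the Arm 1 off-drug biopsies, and the pre-dose PK sample at that visit is affected in the same way.

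The Arm 2 sample remains off drug throughout the window, although its week off could run from 4 to 10 days if dosing moved with the visit. The practical effect depends on whether Arm 1 is enrolled: Protocol 5.4.4 opens both arms concurrently, but the SAP tabulates only the other schedule.

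**What to change.** 1. Reconcile the Cycle X Day 1 window in Appendix 9 with the off-days stated for each arm in 5.4.4 and footnote k, and say whether dosing moves with the visit. Which passage prevails is for the sponsor to decide.
2. Give the C2D1 off-drug biopsy and the pre-dose PK sample their own sampling window, defined by time since last dose and with no early side. On the schedules as written, the nominal intervals are 96 h in Arm 1 and 192 h in Arm 2.
3. Derive time since last dose from the dosing and sampling times already recorded, and state that samples outside that window are not analysed as off drug. This rule should also appear in whatever plan governs the vendor-reported biopsy data.

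The cost is one footnote and one derivation line, with no new data collection. Sites lose a little visit flexibility.
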